## **2.0 Background\***

### *2.1 Scientific or scholarly background and Significance.*

Hematopoietic stem cell transplantation (HSCT) is the transplantation of stem cells (either from the patient themselves [autologous], or a donor [allogeneic]) derived from bone marrow or from peripheral or cord blood for the treatment of blood or bone marrow

**PROTOCOL TITLE: Development of a positive psychology intervention to improve mood and health related quality of life in patients post hematopoietic stem cell transplantation- Proof of Concept Trial**

malignancies including leukemias, lymphomas, myelodysplastic syndromes and myelomas. About 22,000 HSCTs take place annually in the United States.

Adherence to frequent clinic visits, active medication management and health behaviors such as healthy diet and regular physical activity is essential for a successful routine follow-up care after HSCT. Additionally, HSCT patients and their caregivers are required to constantly monitor for risks and symptoms of infections, graft vs. host disease, or relapse, and such vigilance requires high psychological well-being and motivation.

Most HSCT patients are not clinically depressed. However, many experience deficits in psychological well-being (e.g., optimism or positive affect). Low levels of positive states and constructs contribute to fatigue and reduced physical functioning, which inevitably can negatively impact the successful adherence to the intensive follow-up care required after HSCT, health-related quality of life and overall long-term recovery. Importantly, positive states and depression are not simply mirror images of each other (and are only modestly inversely correlated), and the beneficial effects of positive states on outcomes in medical illnesses persist even after accounting for depression/negative affect. This suggests that it is not simply an absence of depression that confers the benefit associated with positive emotions. Indeed, in a wide variety of chronic medical conditions, positive psychological interventions (including exercises to cultivate gratitude, acts of kindness, recall positive life events, and express optimism) completed in a systematic deliberate manner have been prospectively linked to improved well-being, reduced distress/depression, improved medication adherence, and more physical activity.

Although PP states have been shown to positively impact the adherence to health behaviors in patients with chronic medical illnesses, it has not been studied in HSCT patients. Also, there is minimal understanding and report of the deficits in positive emotional states (e.g., optimism or positive affect) in HSCT patients. Additionally, interventions that help boost PP states in HSCT patients have been minimally studied despite their well-documented overall efficacy in other medical populations. We have completed a systematic review of the literature on PP constructs and interventions in HSCT; our review did not yield any preexisting studies that have used PP interventions in any HSCT population.

A PP intervention, consisting of simple, enjoyable exercises that can be delivered via phone by clinicians with a wide range of training, may provide substantial benefit. PP states have been prospectively linked with superior long-term health outcomes and survival in medically ill persons, independent of medical or socio-demographic variables. Additionally, the prospective association between positive states and mortality demonstrated in patients with chronic medical conditions is usually independent of negative emotional states and relevant medical factors. Although PP interventions are easy to deliver and could boost mood and health-related quality of life (HRQoL) in many HSCT patients, they have never been tested in this population.

## *2.2 Prior Experience and gaps in current knowledge.*

Prior to this work with HSCT patients, [name] has been the site principal investigator for observational and intervention studies as well as randomized control

**PROTOCOL TITLE: Development of a positive psychology intervention to improve mood and health related quality of life in patients post hematopoietic stem cell transplantation- Proof of Concept Trial**

trials focusing on positive psychological states and PP interventions in acute coronary syndrome patients to improve cardiac health behaviors.

[name] has also just completed qualitative research (Protocol # 17-154) in HSCT patients at the DFCI to learn more about the psychological experiences (both positive and negative) of patients who have hematologic malignancies who have received HSCT. [name] successfully enrolled 25 patients for 30-60 minute interviews at two time points. Hence she has experience recruiting this patient population, administering validated questionnaires and instruments in addition to working with these patients clinically on the inpatient psychiatry consult service. [name] attends the weekly HSCT team meetings, interfaces with the various clinicians who care for this patient population and has gained familiarity with the patient population, their hospital course after transplant and some of the challenges associated with the immediate recovery phase.

[name] is currently working on a systematic review on the association of positive psychological constructs on various psychological and medical outcomes in HSCT- to her knowledge there are no current systematic reviews looking at the association between positive psychological constructs in HSCT.

As mentioned in an earlier section, although PP interventions have been shown to positively impact different psychological and functional outcomes in other chronic medical populations, it has not been studied in HSCT. We hope to address this gap in knowledge by testing the feasibility and impact of a novel PP-based intervention that has been adapted for HSCT patients. It is our hope that this PP intervention will provide a breadth of significant health benefits for HSCT patients and their well-being.

**2.3      *Relevant Preliminary Studies.***

In the first phase of the treatment development (Protocol # 17-154), we aimed to explore and understand the deficits in positive psychological states in this population to inform the creation of our novel PP intervention for HSCT patients. We have successfully performed qualitative interviews (N=25) in approximately the first 30 to 100 days post HSCT to learn about: a) the emotional states (both positive and negative), health behaviors, quality of life and function, b) the sources of emotional states, c) potential links between positive emotional deficits and quality of life and function and d) the utility of potential PP exercise in HSCT patients.

Some of the lessons from the preliminary analysis of the first phase of the study are outlined as follows: 1) Patients embraced the opportunities to share about their experiences with HSCT; 2) Patients experience both positive and negative emotions as part of the HSCT recovery and these emotions impact patient's overall function and quality of life; 3) Patients are interested in increasing positive emotions during HSCT recovery; and 4) The burden of side effects and complications in the first 60 days post HSCT varies significantly among patients and may be challenging for patients to actively participate in an intervention. With the information from our qualitative research phase

**PROTOCOL TITLE: Development of a positive psychology intervention to improve mood and health related quality of life in patients post hematopoietic stem cell transplantation- Proof of Concept Trial**

and existing literature, we have developed a customized, PP health intervention for HSCT patients.

In the current phase of the treatment development (Phase 2: Refining the intervention), we will perform a proof-of-concept trial (N=25) to ensure our intervention's initial feasibility and to refine the intervention for a larger pilot study.

Essentially, for this phase of the project we hope to do the following:

1. Test an 8-week, telephone-delivered PP intervention in a brief, non-randomized, proof-of-concept trial (N=25).
2. Determine whether this initial intervention is feasible and acceptable in this cohort of HSCT patients.
3. Explore potential benefits of the intervention on outcomes of interest (e.g., optimism, positive affect).

### **3.0 Inclusion and Exclusion Criteria\***

Study participants will be adult (age  $\geq 18$ ) English speaking patients with hematologic malignancies recruited from the Dana Farber Cancer Institute (DFCI) HSCT Program who have access to a phone. Eligible study participants will be identified during the weekly HSCT program meeting, where all transplant attending physicians, physician assistants, nurse practitioners, and infectious disease clinicians review all the upcoming scheduled admissions and discharges as well as the hospital course of admitted patients. Patients who have been approved for the study by their transplant attending physicians at the DFCI weekly transplant meeting who are clinically stable during their HSCT hospitalization will be approached by principal investigator. Willing patients will be told the details of the study and inclusion/exclusion criteria will be assessed. Eligible study participants will then be consented and screened for the study.

The DFCI will register eligible participants in the Clinical Trials Management System (CTMS) OnCore as required by DF/HCC SOP REGIST-101. When required by REGIST-101, registration must occur prior to the initiation of protocol-specific procedures or assessments.

Inclusion Criteria:

- Adult patients with hematologic malignancies hospitalized for allogeneic HSCT at the DFCI inpatient units who are medically stable and appropriate for study approach.
- Ability to speak, read and write English
- Access to a telephone

Exclusion Criteria:

- Current major depressive episode, bipolar disorder, psychosis or active substance use disorder diagnosed via the Mini International Neuropsychiatric Interview (MINI) given that they require more intensive

**PROTOCOL TITLE: Development of a positive psychology intervention to improve mood and health related quality of life in patients post hematopoietic stem cell transplantation- Proof of Concept Trial**

psychological and psychiatric care. We will however enroll patients with moderate mood and anxiety symptoms as they are likely to benefit from a PP intervention and incorporating their experiences will be useful.

- Cognitive deficits impeding a study participant's ability to provide informed consent or participate adequately in the study assessed via a commonly used 6-item cognitive assessment with the Brief Interview for Mental Status (BIMS) screening tool that is sensitive and specific for screening for cognitive impairment in research subjects.
- Medical conditions precluding interviews.

*Special Populations*

- Individuals who are unable to consent or are not yet adults (including infants, children, teenagers), pregnant women or prisoners will be excluded from the study

**4.0 Study-Wide Number of Subjects\***

We are recruiting 25 patients from only one site. This is not a multisite study.

**5.0 Study-Wide Recruitment Methods**

This is not a multicenter study and all subjects will be recruited from one local site.

**6.0 Multi-Site Research**

This study is located to one study site which is the DFCI main campus in Longwood.

**7.0 Study Timelines\***

*7.1 Subject Participation in the study*

The planned duration of total participant participation in the intervention is 24 weeks, broken down as follows: at weeks four, eight and twelve following consent and eligibility determination, participants will receive check-in/psychosocial support phone calls about their recovery, then week 14 is for self-assessment questionnaires prior to the 8-session weekly positive psychology treatment, and the last week will be used for a repeat of self-report measures obtained at baseline. Patients will also be given the option to complete self-reported measures via mail vs. phone.

**PROTOCOL TITLE: Development of a positive psychology intervention to improve mood and health related quality of life in patients post hematopoietic stem cell transplantation- Proof of Concept Trial**

Based on prior recent experience with recruitment from this patient population, we anticipate about 6-months for the total number of patients for the study.

We are estimating the study will be completed in June 2019.

	Enrollment	Check-In/Psychosocial support phone calls (weeks, 4, 8, 12)	Pre-Intervention Visit	Week 1 of PP-intervention	Week 2 of PP-intervention	Week 3 of PP-intervention	Week 4 of PP-intervention	Week 5 of PP-intervention	Week 6 of PP-intervention	Week 7 of PP-intervention	Week 8 of PP-intervention	Follow-Up Session
HSCT team meeting review to confirm eligibility	X											
Assessment of inclusion criteria	X											
Obtain Consent	X											
10-min phone call		X										
PP exercise				X	X	X	X	X	X	X	X	
Follow-up session												X
Self-report measures (LOT-R, PANAS, HADS, PROMIS-PF-20, PROMIS-Fatigue-8a, FACT-BMT)	X		X									X

## 8.0 Study Endpoints\*

Primary Endpoint: Establishing the positive psychology intervention feasibility and acceptability in HSCT patients will be the primary endpoint.

Secondary Endpoint: Assessing the immediate impact of the PP intervention on participants' positive psychological state and psychological well-being (as measured by dispositional optimism, positive affect, anxiety and depression, adherence and functional outcomes) will be the secondary endpoint.

There are currently no anticipated primary or secondary safety endpoints.

## 9.0 Procedures Involved\*

### 9.1 Study Design

**PROTOCOL TITLE: Development of a positive psychology intervention to improve mood and health related quality of life in patients post hematopoietic stem cell transplantation- Proof of Concept Trial**

The goals of this study are to assess the feasibility, acceptability and preliminary impact of this novel 8-session weekly PP-based intervention for HSCT patients.

Patients will be approached close to their discharge from the hospital after their HSCT for eligibility determination and to obtain consent. After consent is obtained, eligibility will be determined with the mini international neuropsychiatric interview (MINI) and a brief cognitive assessment (with the BIMS) to exclude patients who need more intensive psychological or psychiatric care or have cognitive deficits. Upon agreement and consent to participate in the study, participants will receive check-in/psychosocial support phone calls at weeks four, eight and twelve to provide support and check-in on how their recovery is going since discharge, develop rapport and prepare them for the positive psychology treatment portion of the intervention which will start between Day 90-120 post HSCT. Between the 90-120-day point, when patients return to the clinic for their routine 100-day post HSCT follow-up, the interventionist/principal investigator will meet briefly with the patients in clinic to complete self-assessment questionnaires to measure positive affect, optimism, anxiety, depression, HSCT-specific health related quality of life, adherence and overall function. For the rare situations when participants cannot complete these self-assessment questionnaires in person, patients will be given the option to complete self-assessment questionnaires by phone or mail.

After completion of the questionnaires, participants will be provided with a treatment manual, with weekly PP exercises for 8-sessions. All participants will be asked to complete 8 weekly PP exercises and will be asked to speak with the study interventionist, in this case the principal investigator, weekly. Immediately after the completion of the exercises, the participants will rate the ease of exercise completion, overall utility of the exercise, and their current levels of positive affect. For the last week of the intervention, baseline self-assessment questionnaires will be reviewed. At study completion, we will inquire about participants' potential interest in being contacted about our future studies. We will adhere to any and all participant requests regarding contact.

## 9.2 *Research Procedures*

**Psychosocial Support/Check-In phone calls:** Study participants will receive monthly phone calls from the study interventionist/principal investigator at weeks four, eight and twelve following their enrollment. The goal of the psychosocial support/check-in phone calls is to provide study participants an avenue to talk about their adjustment and transition to the outpatient care from inpatient, quality of life and coping during recovery, adherence to treatment, etc...which will be beneficial to patients

**PROTOCOL TITLE: Development of a positive psychology intervention to improve mood and health related quality of life in patients post hematopoietic stem cell transplantation- Proof of Concept Trial**

and help with rapport building with the interventionist prior to the positive psychology intervention.

**Pre-intervention visit:** The first physical contact with the patient since consent and enrollment during the HSCT hospitalization will be at the routine 100-day follow-up visit (around Day 90-120) in clinic. The visit will happen in a private room at in the DFCI outpatient clinic. Patients will complete the following self-assessment scales: Positive and Negative Affective Scale (PANAS) to measure positive affect, Life Orientation Test-Revised [LOT-R] to measure optimism and the Hospital Anxiety and Depression Scale [HADS] to measure anxiety and depression. We will also assess HSCT-specific HRQoL with the Functional Assessment of Cancer Therapy-Bone Marrow Transplantation [FACT-BMT] scale), overall function (PROMIS-PF-20), and fatigue (PROMIS-Fatigue-8a). Data about medical and oncologic history, treatment course and medications will be obtained from the electronic medical record. – A waiver of HIPAA authorization would be requested for this and will only be clarified with patients if there are inconsistencies in the medical records. This in person session should take about 30 minutes. Patients will also be given the option to complete this visit over phone if in person visit cannot be coordinated with other routine 100-day follow-up care.

After completion of the questionnaires, participants will be provided with a treatment manual, with weekly PP exercises. Participants will be assigned the first exercise (gratitude for positive events) in preparation for their first phone session.

**Weekly phone sessions for positive psychology intervention:** All participants will be asked to complete 8 weekly PP exercises and to speak with the interventionist weekly. Weekly phone sessions will last approximately 30 minutes. Prior to completing each phone session, participants will be asked to rate their current level of happiness and optimism, using a 10-point Likert scale. Immediately after completing the exercise and phone session, participants will rate the ease of exercise/session completion, overall utility of the exercise/phone session, and their current levels of happiness and optimism, all using 10-point Likert scales. These calls will be recorded so that a percentage (10%) of these recordings can be reviewed by research mentor, [name] to ensure that the PP intervention is being delivered as described in the protocol.

**Follow-up session:** The last week of the study will be used for a repeat of the self-assessment questionnaires obtained at the beginning of the study. This will be done either via phone or mail depending on patient preference.

**Positive Psychology Program Content.** All phone sessions will include (a) a review of the ease and utility of the week's PP exercise (b) a discussion of the

**PROTOCOL TITLE: Development of a positive psychology intervention to improve mood and health related quality of life in patients post hematopoietic stem cell transplantation- Proof of Concept Trial**

rationale of the next week's PP exercise through a guided review of the PP manual, and (c) assignment of the next week's PP exercise. During the calls, the interventionist and participant will also review the next section of the treatment manual and prepare for the upcoming week's exercise.

**Positive Psychology Exercises.** The PP exercises used in this study were selected based on the qualitative study results from the first phase of this study (IRB: 17-154), their superior performance in our pre-pilot research and others' work with medical populations. They will be grouped into three modules focusing on a different psychological state:

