### *1.3 Hypothesis*

**Hypothesis #1:** The PP exercises will be feasible (i.e., 5 of the 8 phone sessions will be completed by a majority of patients) and acceptable (mean score of at least 6 out of 10 on ratings of ease of completion and subjective utility of the exercises). Furthermore, we will obtain complete objective follow-up data in at least 80% of enrolled participants at the end of the intervention.

**Hypothesis #2:** The intervention will lead to improvements in positive affect and other psychological well-being factors as measured by dispositional optimism, anxiety, and depression at completion compared to baseline.

**Hypothesis #3:** The intervention will lead to improvements in health-related quality of life and functional outcomes at completion compared to baseline.

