**Follow-Up Session**

At the last week of the study, a member of the study staff will call participants to repeat the self-report questionnaires that were administered at baseline. Positive and Negative Affective Scale (PANAS) to measure positive affect, Life Orientation Test-Revised [LOT-R] to measure optimism and the Hospital Anxiety and Depression Scale [HADS] to measure anxiety and depression. We will also assess HSCT-specific HRQoL with the Functional Assessment of Cancer Therapy-Bone Marrow Transplantation [FACT-BMT] scale), fatigue (PROMIS-Fatigue-8a) and overall function (PROMIS-PF-20). Finally, patients will be asked about their experience in the study, including any aspects of the intervention or study procedures that could be improved. In sum, these scales should take approximately 30-40 minutes to complete. If participants would rather complete the follow-up questionnaires in written form rather than over the phone, we will send them a paper packet at the time of the follow-up.

Given the results of our prior PP studies in medical populations yielding a 64-85% completion rate of the exercises, and given that this is a feasibility study (i.e., we want to assess participants' willingness to complete the phone sessions), we will expect participants to complete at least 5 PP exercises. In other words, if a participant completes at least 5 sessions, missed sessions will not be considered a deviation from the protocol.

**Training.** The PP exercises for this trial have been identified via published literature, or directly from researchers, and modified appropriately for this population based on results from first phase of the study that the IRB approved (17-154). Additional text outlining the rationale and instructions for each exercise are in the written packets for each exercise that are provided to participants. [name] will engage in several training exercises prior to study initiation. [name] research mentor, [name], and his research group have had substantial experience in explaining and delivering PP exercises from their studies in cardiac and psychiatric patients, which will inform [name] training. Together with [name], [name] will review the treatment manual and the team's prior training manuals related to these exercises. They then will complete all exercises together to gain experience performing and reviewing each exercise.

*9.3 Procedures performed to lessen the probability or magnitude of risks.*

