**20.0 Resources Available**

**PROTOCOL TITLE: Development of a positive psychology intervention to improve mood and health related quality of life in patients post hematopoietic stem cell transplantation- Proof of Concept Trial**

The principal investigator has experience recruiting from this patient population and most recently with the successful recruitment of patients for study (IRB 17-154). The PP exercises for this trial have been identified via published literature, or directly from researchers, and modified appropriately for this population based on results from first phase of the IRB approved (17-154). [name] will engage in several training exercises prior to study initiation. [name] research mentor, [name], and his research group have had substantial experience in explaining and delivering PP exercises from their studies in cardiac and psychiatric patients, which will inform [name] training. Together with [name], [name] will review the treatment manual and the team's prior training manuals related to these exercises. They then will complete all exercises together to gain experience performing and reviewing each exercise.

We have decided to recruit 25 patients for this feasibility study based on experience from other studies in medical populations involving positive psychology exercises. In the first phase of the study, we recruited 25 patients, a month earlier than our recruitment timeline, an indication that recruiting 25 patients for the feasibility study is reasonable. The DFCI HSCT sees approximately 550 patients annually for a transplant so we are targeting only 1.8% of the patients that come through the HSCT program.

We will also have research assistants who will help with different aspects of the study including organizing materials for the intervention, managing databases, coding qualitative interviews, performing data analysis and organizing documentation for the study.

I will be devoting 40-50% of my productivity time to this research.

Patients will be seen for consent in their private BWH inpatient rooms. They will be seen for baseline data collection in a private outpatient consulting room at the DFCI. All phone communications will be done using DFCI phones.

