If patients report acute medical symptoms, they will be directed to emergency medical care, and their primary medical and transplant oncologists may be contacted as needed. If the patient is at imminent risk to self-harm, the study psychiatrist will take all needed steps to ensure emergent psychiatric evaluation, which may include ensuring evaluation in the nearest emergency room. Participants will be informed of these measures to ensure confidentiality—and the limits of confidentiality, such as arranging for emergent medical or psychiatric care if safety is at imminent risk—as part of the informed consent process. However, given that this is a medical rather than a psychiatric population we anticipate the rate of suicidality in this population will be low.

**PROTOCOL TITLE: Development of a positive psychology intervention to improve mood and health related quality of life in patients post hematopoietic stem cell transplantation- Proof of Concept Trial**

All study staff for the project will meet weekly to discuss progress of the study and to review any changes in the protocol. Currently, the PI is the only study staff but as research assistants come on board to enter and manage databases such as RedCap, the IRB will be notified, they will be oriented to the details of the study protocol, as well as their individual roles in data collection and management.

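### The weekly ratings behind the 6/10 acceptability criterion follow a call in which the interventionist reviews ease and utility, and 9.2 words the item to cover the call as well as the exercise

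*Combined protocol and SAP*

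**What the plan says.** Acceptability belongs to the primary aim (section 1.2) and the primary endpoint (section 8.0). Section 1.3 sets the criterion: "mean score of at least 6 out of 10 on ratings of ease of completion and subjective utility of the exercises". Section 11.1 reports mean exercise ratings descriptively, with no test or interval attached to the threshold.

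Under section 9.1, participants "will be asked to speak with the study interventionist, in this case the principal investigator, weekly". Before that, the same person makes check-in calls at weeks 4, 8 and 12, which section 9.2 intends partly to build rapport.

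On the content of the weekly calls, section 9.2 says "All phone sessions will include (a) a review of the ease and utility of the" week's exercise. The same section places the rating directly after the exercise and the phone session, on 10-point scales, and one rated item is "overall utility of the exercise/phone session". Section 9.1 instead places the rating directly after the exercises and names only the ease and utility of the exercise.

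Neither section says who takes down the score or by what route. The planned review of 10% of recordings checks that the intervention is delivered as described, not how ratings are obtained.

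**The concern.** The two quantities in the criterion are the same two that the participant has just talked through with the person delivering the treatment, someone who has been phoning in a supportive role for about three months. Two things could raise the score: courtesy towards that person, and, because the 9.2 item covers the session too, a good call being counted as a good exercise. Both would be expected to push upwards. The trial has one arm, so no comparison group would reveal an inflated level.

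The stake is the decision that the study exists to inform. A set of exercises that participants find only middling could pass 6/10 and go unchanged into the larger pilot. Even where the verdict is right, a combined item makes it harder to see which exercises need work, and refining the intervention is a stated aim in section 2.3.

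**Working it through.** **1. No figure to reproduce.** The plan gives no expected mean, standard deviation or bias estimate for the ratings.

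**2. The texts side by side.**

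| Place | What is rated | When | Who records it |
|---|---|---|---|
| 1.3 (criterion) | exercises | not stated | not stated |
| 9.1 | exercise | directly after the exercises | not stated |
| 9.2 | exercise/session | after exercise and phone session | not stated |
| 11.1 (analysis) | exercise ratings | not stated | not stated |

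The 9.2 item is wider than the criterion and the analysis, and its timing differs from 9.1. On the 9.1 reading the score can be given before the call; on the 9.2 reading it comes after ease and utility have been discussed with the interventionist.

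**3. Illustration of how sensitive the threshold is.**

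- From the documents: threshold 6 (section 1.3); n = 10, the anticipated completers (sections 11.2 and 23.0).
- Assumed: SD of a participant's mean rating 2 (range 1.5 to 2.5); true mean m of 4.5, 5.5 or 6.5 (5.5 is the midpoint if the scale runs from 1 to 10, which the plan does not state); upward shift b of 0, 0.5 or 1 point; one mean per participant; normal approximation.

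P(observed mean ≥ 6) = 1 − Φ((6 − m − b) / (SD/√n)), with SD/√n = 2/√10 = 0.632.

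For m = 5.5:
- b = 0: 0.5/0.632 = 0.791, so P = 21%
- b = 0.5: 0/0.632 = 0, so P = 50%
- b = 1: −0.5/0.632 = −0.791, so P = 79%

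| True mean | No shift | +0.5 | +1 |
|---|---|---|---|
| 4.5 | 1% | 6% | 21% |
| 5.5 | 21% | 50% | 79% |
| 6.5 | 79% | 94% | 99% |

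At m = 5.5, varying SD from 1.5 to 2.5 gives 15–26%, 50% and 74–85%. With all 25 enrolled as raters and SD 2, the row is 11%, 50% and 89%.

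**4. Reading it.** Only the sum m + b matters, so the 50% entry is arithmetic (5.5 + 0.5 = 6), not a finding. A shift of half a point to one point changes the outcome mainly when the true mean lies just below 6. At 4.5 a full point still leaves a 21% chance of passing; at 6.5 the criterion is met 79% of the time with no shift at all.

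**The case against.** The strongest reply is that the central step is inferred. A reader might take the plan to say that the interventionist hears or writes down the score. It does not: 9.2 describes a review of ease and utility on the call and, separately, a rating afterwards, and the collector is unstated. That stands. The supported statement is that the rating follows the discussion and that the collection route is not specified.

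A reader might also infer that the investigator collects follow-up and so biases the 6/10 result. The Follow-Up Session text says "a member of the study staff will call participants to repeat the self-report questionnaires", and section 20.0 says "Currently, the PI is the only study staff". But the same section also says "We will also have research assistants who will help with different aspects of the study", and a paper packet is offered. More to the point, the criterion rests on ratings of the exercises, not on the follow-up scales, so follow-up collection cannot affect it. At most it touches the Aim 2 and 3 scales and the closing questions about study experience.

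A third reply is that the probabilities show how a threshold behaves and do not show that bias exists. That is correct, and it is why the true mean is varied above.

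Finally, one might want scores hidden from the interventionist until follow-up ends. This would conflict with the weekly review of acceptability information in section 11.4 and with the investigator's checking of REDCap entries in section 11.3. It is not needed.

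What survives is that 9.2 departs from 1.3 and 9.1 on what is rated, and that a primary measure has no stated, private route of collection. The descriptive, unpowered nature of the study lowers the stakes but does not remove either point.

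**Conclusion.** The point holds as a risk of upward bias in a primary measure, together with a mismatch between the rated item and the criterion. The mismatch can be read directly from the text. The size of the bias cannot be derived from the documents: the SD, true mean and shift used above are all assumptions. Under them, a courtesy shift of 0.5 to 1 point could decide the result if true acceptability is just under 6, and would matter much less if it is well below or already above. The documents do not support the stronger claims that the investigator records the scores or that follow-up collection distorts the 6/10 criterion. This is a cheap improvement to the plan, not a demonstrated failure of it.

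**What to change.** In sections 9.1 and 9.2:

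- Have participants write the exercise ease and utility ratings themselves, on a page in the treatment manual, directly after the exercise and before the call reviews it. This follows the timing that 9.1 already implies.
- Have the page returned by mail or form, not spoken to the interventionist. The call can still discuss the exercise.
- Use separate items for the exercise and for the phone session, and state that the 6/10 threshold applies to the exercise items only.
- State who enters the ratings in REDCap. The weekly acceptability review in 11.4 continues, using the pages returned so far.

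For the Aim 2 and 3 scales, encourage self-completion on the paper packet already offered.

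The cost is protocol wording, a page in the manual, two extra short items a week and possibly a few more missing ratings. The change does not make the scores confidential, since the investigator still reviews the data; it removes the need to voice them to the person who delivered the session. If some participants have already rated the combined item, report their ratings separately.
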